**The Effects of temporary ileostomy on outcome in
patients with rectal cancer, A prospective
Comparative Cohort Study protocol**

NCT number: not available yet

Date: 10/9/2021

Background

Colorectal cancer(CRC) represents the most common type of gastrointestinal cancer [1]. It is the third most commonly diagnosed cancer in males and the second in females according to the World Health Organization (WHO), with various rates of incidence around the world [2]. CRC is a multifactorial disease process that includes genetic factors, environmental exposures, and inflammatory diseases [3]. There is an improvement in outcome and death rates have declined progressively which can be attributed to early detection and removal of CRCs in earlier stages and effective adjuvant therapy [4]. Surgery is considered currently the definitive treatment modality for rectal cancer, and surgical intervention is performed either by local or radical excision depending on the clinical stage, size, and location of the primary tumor [5].

There are many techniques to be used including local excision, low anterior resection(LAR), abdominoperineal resection, and multi-visceral resection [6]. LAR represents a sphincter-sparing resection and is performed in patients who meet all the following criteria: invasive rectal cancer, the ability to perform negative distal margin, and an adequate anorectal sphincter function before surgery [7]. Numerous postoperative complications can significantly lead to morbidities, prolonged hospitalization, and even mortality, and management of these complications can be beneficial for survival rate and improvement of quality of life [7]

Anastomotic leakage(AL) represents a frequent complication after LAR in patients with rectal cancer and is responsible for significant morbidity and mortality. The incidence of AL varies from 3 to 21% with a high rate of mortality despite improvements in

surgical techniques [8]. In addition, AL is associated with worsened functional outcomes, reduced quality of life, and increased financial burden. Risk factors for AL include more distal anastomoses, neoadjuvant pelvic radiation therapy, male gender, prolonged operative time, advanced stage of tumor, and multiple firings of linear stapler across rectal stump [9]. The role of a protective stoma has been debated. Therefore, the aims of our study were: 1- to evaluate the effect of temporary ileostomy on the occurrence of AL, 2-to compare complications between patients according to the presence of protective ileostomy.

Methodology

Patients

This is a prospective comparative study of a group of patients with a diagnosis of colorectal cancer of both sexes and all ages that required low anterior resection(LAR) attending the Department of General Surgery at Tishreen University Hospital in Lattakia-Syria during the two years (May 2021- May 2023). The exclusion criteria are patients who undergo abdominoperineal resection with permanent ileostomy. The following workup included: a history and physical examination.

Preparation of the bowel is performed before surgery with the administration of intravenous perioperative antibiotic prophylaxis. The surgical procedure is performed by laparotomy, with resection of the rectum and mesorectum (TME) up to the level of the pelvic diaphragm, sparing the autonomic nerves. End-to-end anastomosis is performed either with a stapler or by hand-sewn. Patients are assigned to group I (19 patients) who will undergo temporary ileostomy, and group II (28 patients) who will not undergo ileostomy. Patients are followed up at regular intervals and outcomes were compared between two groups.

Data collection

the following data will be collected through clinical examinations, patient interviews, and medical records including : Demographic data including : Age as Continuous variable measured in years, Sex as Categorical variable (Male/Female), Tumor Stage as Categorical variable representing the clinical stage of colorectal cancer, Radiotherapy as Binary variable indicating whether the patient received radiotherapy before surgery. The Surgical Characteristics are : the Type of Anastomoses as

Categorical variable (Hand-sewn/Stapled), and Protective Ileostomy as Binary variable indicating the presence or absence of a temporary ileostomy. The Outcomes which will be measured are : the Duration of Surgery as Continuous variable measured in hours, the Anastomosis Leakage as Binary variable indicating the presence or absence of leakage, the Surgical Site Infection as Binary variable indicating the presence or absence of infection, and the Local Recurrence as Binary variable indicating the presence or absence of local recurrence.

Patients will be followed for 30 days after surgery to assess short-term outcomes. Assessments will be conducted at regular intervals to monitor the occurrence of outcomes.

Ethical Considerations

Written informed consent will be obtained from the patient for publication and any accompanying images. A copy of the written consent is available for review on request. Ethical approval for this study (Ethical Committee 2021-GS-104) was provided by the Ethical Committee of Tishreen University Hospitals, Latakia, Syria on 10 October 2021. In addition, the investigators ensure that the study conforms to the principles of the Declaration of Helsinki (last revised in 2013) and is conducted in accordance with the ICH Guideline for Good Clinical Practice.

Statistical Analysis Plan

Statistical analysis was performed by using the IBM SPSS version. Basic Descriptive statistics included means, standard deviations(SD), median, Frequency, and percentages. To examine the relationships and comparisons between the two groups, the chi-square test was used. Independent t student tests were used to compare 2 independent groups. All the tests were considered significant at a 5% type I error rate($p<0.05$), $\beta:20\%$, and power of the study:80%.

References

1-Saltz L. Top advances of the year in colorectal cancer. *Cancer* 2022;128:2236-2239.

2-WHO. Cancer. Available online: [https://www.who.int/news-room/fact-sheets/detail/cancer\(2021\)](https://www.who.int/news-room/fact-sheets/detail/cancer(2021)).

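### Aim 2 compares complications by ileostomy, but the outcome list has no field for any stoma-related event, reoperation, readmission or death

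*Combined protocol and SAP*

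**What the plan says.** Background ends with two aims. The first is "1- to evaluate the effect of temporary ileostomy on the occurrence of AL"; the second is "2-to compare complications between patients according to the presence of protective ileostomy". Neither the aims nor the Statistical Analysis Plan defines which complications are meant. The Statistical Analysis Plan names tests but no outcomes.

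The outcomes to be measured are set out in Data collection, and there are four:

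- operating time, in hours
- leakage from the anastomosis, yes or no
- infection, given only as "the Surgical Site Infection as Binary variable indicating the presence or absence of infection"
- recurrence at the local site, yes or no

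The only stated length of follow-up is in the same section: "Patients will be followed for 30 days after surgery to assess short-term outcomes". The ileostomy appears there as a yes/no surgical characteristic and nowhere as a source of outcomes. It is described as temporary, but its closure is neither scheduled nor recorded. Background also remarks, in general terms, that "Numerous postoperative complications can significantly lead to morbidities, prolonged hospitalization, and even mortality".

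**The concern.** The protocol says that the role of a protective stoma is debated, and aim 2 asks how complications compare with and without one. Answering that needs outcomes on both sides. The expected benefit, fewer leaks, has a field. Complications that can arise only because a stoma is present have none, and neither do the general events through which serious complications usually show themselves (reoperation, readmission, death).

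A team that followed the plan exactly could report that ileostomy did not increase complications without having looked for any complication of the ileostomy. That would leave one of the study's two stated aims answered from one side only.

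**Working it through.** The plan gives no figure on this point to reproduce, so the main check sets the outcome list against aim 2.

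| Listed outcome | A complication? | Assessable at 30 days? | Specific to the stoma? |
|---|---|---|---|
| Duration of surgery | No, an operative measure | Yes | No |
| Anastomotic leakage | Yes (also the subject of aim 1) | Yes | No |
| Surgical site infection | Yes | Yes | No |
| Local recurrence | No, an oncological event | Not usefully | No |

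The entries on local recurrence are a judgement; the documents do not discuss when recurrence can be detected. The count is two complications usable for aim 2 and no stoma-specific outcomes. No other section adds one.

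**How many events could go unrecorded.** Group I has 19 patients (Methodology, Patients). The documents give no stoma complication rate, so the rate *s* is an assumed range. Expected events are 19 × *s*, and the chance of at least one is 1 − (1 − *s*)^19.

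| Assumed *s* | Expected events | Chance of at least one |
|---|---|---|
| 5% | 19 × 0.05 = 0.95 | 1 − 0.95^19 = 62% |
| 10% | 19 × 0.10 = 1.9 | 1 − 0.90^19 = 86% |
| 20% | 19 × 0.20 = 3.8 | 1 − 0.80^19 = 99% |
| 30% | 19 × 0.30 = 5.7 | 1 − 0.70^19 = 99.9% |

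Across this range, at least one event with no field of its own is more likely than not.

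**What the missing fields could show.** If stoma events were recorded and none occurred in 19 patients, the one-sided 95% upper limit for the rate would be 1 − 0.05^(1/19) = 14.6%. The upper limit of a two-sided 95% interval would be 1 − 0.025^(1/19) = 17.6%. The added data would be descriptive: they would show what happened, but could not exclude a moderate rate.

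**List or window?** Stoma complications within 30 days fall inside follow-up and still have no field, so the outcome list is the main cause. The window matters only for complications of closure, and only if closure comes after day 30, which the documents do not say.

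**The case against.** Several counter-arguments carry weight.

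- *Leakage is itself a complication.* Background describes it as one, and nothing makes the two aims mutually exclusive. This stands: aim 2 does not rest on infection alone.
- *The list can show some cost of a stoma.* Longer surgery could appear under duration, and a stoma-site infection might be counted as surgical site infection. This stands in part. Duration is not a complication, and surgical site infection is undefined and would miss non-infectious stoma events.
- *Follow-up is declared to be short-term.* True, but stoma events within 30 days are equally unrecorded.
- *The remark on hospital stay and mortality is general background.* Agreed. It commits the study to measuring neither, and the point does not depend on it.
- *No conclusion about overall stoma harm has been drawn.* Also true; the risk lies in what aim 2 as worded invites.

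Three stronger readings are tempting but not supported. A reader might infer that the study as a whole is biased towards ileostomy. Assignment is not described as random, so confounding could act in either direction. A reader might also set the 3–21% leak incidence in Background against an assumed stoma complication rate and look for the rate at which benefit and harm cancel. That incidence range describes variation between reports; it neither estimates nor bounds the effect of ileostomy, and the calculation would also treat a stoma complication of any grade as equal to a leak. Finally, a reader might infer that longer follow-up is the remedy. By itself it would still leave no field for stoma events.

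**Conclusion.** The point holds as a defect in outcome selection. Aim 2 promises a comparison of complications; the list supplies two that can be assessed at 30 days and none that is specific to the stoma, with no reoperation, readmission or death. A conclusion that ileostomy reduces or does not increase complications would be one-sided to that extent.

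Its size cannot be derived from the documents. The 1.0 to 5.7 expected events among 19 patients rest wholly on the assumed 5–30% range and only show that the omission is unlikely to be empty. The net direction of bias in the study is not established. The change should be made because it decides whether the second aim can be answered even-handedly, and it costs little.

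**What to change.** 1. Add to the 30-day outcome list: stoma-related complications (group I), reoperation, readmission, length of stay and death. Define each in advance, with a severity grade for complications. Word reoperation and readmission so that a planned closure inside the window is not counted as a complication.
2. For aim 2, report any complication within 30 days by group, with every component and its severity shown separately. Report length of stay on its own. Describe the stoma component in group I only, with a confidence interval; it is zero in group II by definition, so a between-group test of it has no meaning.
3. State that the comparison covers 30 days and does not assess later complications of stoma closure. Tabulating closure up to the end of the study should not serve as a comparative result: recruitment runs to May 2023, so late entrants would have little follow-up.
4. If the fields are not added, restrict aim 2 and its conclusion to 30-day leakage and surgical site infection, and state that stoma harm was not assessed.

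The cost is a few more fields from the examinations, interviews and records already used, completed from records for patients already treated, plus some wording in the Statistical Analysis Plan. No extra patients are needed, and no follow-up beyond 30 days. The drawback is a composite with one component that can occur only in group I, which is why the components must always be shown beside it.

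### Height of the anastomosis, the first leak risk factor the plan names, is not recorded, so the unadjusted leak comparison may be confounded by it; the entry wording should also be reconciled with the title

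*Combined protocol and SAP*

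**What the plan says.** - **Title.** The population is "patients with rectal cancer, A prospective" comparative cohort.
- **Methodology, Patients (entry).** The series is "a group of patients with a diagnosis of colorectal cancer of both sexes and all ages that required low anterior resection(LAR"). The one exclusion reads: "The exclusion criteria are patients who undergo abdominoperineal resection with permanent ileostomy". Neither sentence limits tumour height or anastomotic height.
- **Background (who has LAR).** "LAR represents a sphincter-sparing resection and is performed in patients who meet all the following criteria: invasive rectal cancer", followed by conditions on the distal margin and on sphincter function.
- **Methodology, Patients (operation).** One procedure is described for the series: "resection of the rectum and mesorectum (TME) up to the level of the pelvic diaphragm". No distance is given.
- **Background (risk factors).** "Risk factors for AL include more distal anastomoses, neoadjuvant pelvic radiation therapy, male gender, prolonged operative time", followed by tumour stage and repeated stapler firings.
- **Data collection.** Before and during surgery: age, sex, stage, preoperative radiotherapy, hand-sewn or stapled join, and ileostomy yes/no. Outcomes: duration of surgery, leakage, surgical site infection and local recurrence. Height is not on the list.
- **Groups and analysis.** The Patients section assigns 19 patients to ileostomy and 28 to none, with no randomisation and no stated rule. The Statistical Analysis Plan uses chi-square and t tests, with no stratification, matching or adjustment.

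**The concern.** The first aim is the effect of a temporary ileostomy on leakage. In a non-randomised comparison, a strong leak risk factor that is distributed differently in the two groups is read as an effect of the stoma. By the plan's own account, the level of the join is such a factor. It is plausible that surgeons take it into account when deciding on an ileostomy, although the documents do not say so.

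Because height is not collected, a reader of the results could not check whether the groups were alike on it, and the analyst could not adjust for it. Radiotherapy, stage and type of join may be partial stand-ins for height, but no more than that.

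A second, smaller matter is the entry wording. It says colorectal where the title, the Background and the described operation all point to the rectum, so the population to which the result applies is unclear.

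**Working it through.** **Step 1: named risk factors against collected variables.** The Background names six factors. Four are collected: radiotherapy, sex, stage and duration of surgery (the last as an outcome). Two are not: level of the anastomosis and number of stapler firings. The first in the plan's list is therefore one of the two missing.

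**Step 2: can height vary within this series?** The Background criteria for LAR confine the disease to the rectum but set no height. The operation sentence describes how far the resection goes. It narrows the range of joins but gives no distance and is not an entry criterion. The Background also introduces leakage as a complication of LAR for rectal cancer and then lists distal anastomosis among its risk factors, so the plan itself treats height as mattering within this population.

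**Step 3: what could an imbalance do?** The plan gives no figure on this point to reproduce. Inputs from the documents are 19 and 28 patients, and a leak incidence of 3 to 21%. The documents do not break that range down by height, so attaching its ends to high and low joins is an assumption, as are all the shares below.

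Expected leak rate in a group = r × [q × p(low) + (1 − q) × p(high)], where q is the share of low joins and r is the true risk ratio of the ileostomy (r = 1 in group II).

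Worked case, p(low) = 0.21 and p(high) = 0.03:
- Group I, q = 0.9: 0.9 × 0.21 + 0.1 × 0.03 = 0.192
- Group II, q = 0.5: 0.5 × 0.21 + 0.5 × 0.03 = 0.120
- No stoma effect: 0.192 / 0.120 = 1.6
- True halving: (0.5 × 0.192) / 0.120 = 0.096 / 0.120 = 0.8

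| Assumed risk, high / low | Share low, group I / II | No effect (true ratio 1) | Halving (true ratio 0.5) |
|---|---|---|---|
| 3% / 21% | 50% / 50% | 12.0% v 12.0%, 1.00 | 6.0% v 12.0%, 0.50 |
| 3% / 21% | 60% / 40% | 13.8% v 10.2%, 1.35 | 6.9% v 10.2%, 0.68 |
| 3% / 21% | 80% / 40% | 17.4% v 10.2%, 1.71 | 8.7% v 10.2%, 0.85 |
| 3% / 21% | 90% / 50% | 19.2% v 12.0%, 1.60 | 9.6% v 12.0%, 0.80 |
| 3% / 21% | 90% / 30% | 19.2% v 8.4%, 2.29 | 9.6% v 8.4%, 1.14 |
| 8% / 16% | 90% / 50% | 15.2% v 12.0%, 1.27 | 7.6% v 12.0%, 0.63 |

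Equal shares give no bias. If the imbalance ran the other way (40% low in group I, 80% in group II), no effect would appear as 10.2% v 17.4%, a ratio of 0.102 / 0.174 = 0.59. Within either height class the ratio equals r by construction, which is why a stratified comparison helps.

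**Step 4: how much data is there to adjust with?** At the ends of the incidence range, 47 patients yield 47 × 0.03 = 1.4 to 47 × 0.21 = 9.9 leaks. Any adjusted estimate will be imprecise.

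**The case against.** The strongest reply is that the series is already narrow. A reader might infer from the word colorectal that any bowel cancer can enter and that the study knowingly mixes high and low joins. The documents do not support that: entry requires LAR, the Background ties LAR to invasive rectal cancer, and one operation, reaching the pelvic floor, is described for everyone. This part of the reply stands. What remains is loose entry wording, and variation in height within LAR that is unmeasured.

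A reader might also infer that group II must be enriched with high, low-risk joins. The documents state no assignment rule, so neither the existence nor the direction of an imbalance is documented.

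Nor can the ratios above be read as estimates. They attribute the whole of a literature range to height and rest on invented shares. The apparent-harm row amounts to about 1.8 expected leaks in 19 (19 × 0.096) against 2.4 in 28 (28 × 0.084), which could not be told from chance.

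Finally, the root problem is non-random assignment with an unadjusted test, and height is one instance of it. That is so, but height is the factor the plan itself puts first, and it costs one number per patient to collect.

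**Conclusion.** The point holds in a limited form. As written, the plan cannot separate an effect of the ileostomy from a difference in anastomotic level, because a named leak risk factor is left out of the data list and the test is unadjusted. This is more than missing detail, and it should be changed.

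The size is unknown. Under the assumptions shown, with more low joins in the ileostomy group, a null effect appears as a ratio between 1.27 and 2.29, and a true halving as one between 0.63 and 1.14. Equal shares give no bias. These figures show the mechanism only. Without recorded height, nobody could show that the shares were equal.

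It would go too far to say that no analysis of the collected variables could help: they may correct part of the difference, but not all of it. The mismatch between colorectal and rectal is a wording fault that blurs the target population; it does not show that other cancers are being enrolled.

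**What to change.** 1. Add the distance of the anastomosis from the anal verge (cm, from the operation note) to the Data collection list, and report it by group.
2. Beside the unadjusted leakage comparison, present one stratified by or adjusted for height, for example a Mantel-Haenszel or exact stratified analysis with a cut fixed before leaks are examined.
3. State in advance that if height differs between the groups, the conclusion on leakage will be worded as an association. If the groups hardly overlap in height, stratification cannot separate the two effects, and the report should say so.
4. Reconcile the entry criterion with the title and the described operation.

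Do not restrict entry or the main comparison by height:
- With 50% or 30% low joins in group II, restriction to low joins would remove about 14 (28 × 0.5) or 20 (28 × 0.7) of its 28 patients.
- Limiting the comparison to heights found in both groups would not balance height.
- The procedure paragraph gives no distance that could serve as a limit.

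The cost is one data item per patient, some wording, and an adjusted estimate that will be less precise with 47 patients and few leaks.

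### Local recurrence is compared between groups as a yes/no outcome with no stated time point, and the only follow-up length given, 30 days, cannot inform that comparison

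*Combined protocol and SAP*

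**What the plan says.** The Data collection section names four outcomes: duration of surgery, anastomotic leakage, surgical site infection and local recurrence. The entry for the last is "the Local Recurrence as Binary variable indicating the presence or absence of local recurrence", with no time point attached.

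The same section gives the one follow-up length in the document: "Patients will be followed for 30 days after surgery to assess short-term outcomes". The next sentence reads "Assessments will be conducted at regular intervals to monitor the occurrence of outcomes". The Methodology has a similar sentence, which also sets up the comparison: "Patients are followed up at regular intervals and outcomes were compared between two groups". Neither of these two sentences gives an interval or an end point.

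Sources are described for all variables together: "the following data will be collected through clinical examinations, patient interviews, and medical records". Nothing is specific to recurrence.

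The Statistical Analysis Plan says "To examine the relationships and comparisons between the two groups, the chi-square test was used". It names no time-to-event method and no way of handling unequal follow-up. The dates May 2021 to May 2023 describe when patients attended the department, not how long each was followed.

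The aims, at the end of the Background, are leakage and, second, "2-to compare complications between patients according to the presence of protective ileostomy". Recurrence is not named in either.

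**The concern.** A yes/no outcome that accumulates over time means nothing until one knows by when. The text leaves three readings open.

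1. Recurrence is scored within the stated 30 days. Almost no events can be expected, so the comparison is uninformative.
2. Recurrence is scored at one common calendar date. The documents state no such cut-off, so this is an inference. Patients operated on at different times would then have different time at risk, and a chi-square test on crude proportions ignores that.
3. Recurrence is scored at a fixed later time with complete follow-up. A yes/no comparison would then be acceptable in form, but no such time is stated.

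Under the first reading, a report of no difference in local recurrence would say nothing about ileostomy, yet could be taken as oncological reassurance. Under the second, the proportions mix recurrence with length of observation.

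**Working it through.** **Inputs from the documents.** Groups of 19 (ileostomy) and 28 (no ileostomy), total 47; 30-day follow-up; chi-square test; 5% significance level (two-sided assumed, as sidedness is not stated). The 80% power in the Statistical Analysis Plan has no endpoint or effect size attached, so there is no stated figure for recurrence to reproduce.

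**Assumption.** The documents give no recurrence rate. I take a two-year risk r of 5%, 10% or 20%, a constant hazard, and the same risk in both groups.

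**Reading 1: 30 days.** Monthly hazard h = −ln(1−r)/24. 30-day risk = 1 − exp(−h × 30/30.44).

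| Two-year risk | 5% | 10% | 20% |
|---|---|---|---|
| h per month | 0.00214 | 0.00439 | 0.00930 |
| 30-day risk | 0.21% | 0.43% | 0.91% |
| Expected events in 47 | 0.10 | 0.20 | 0.43 |
| Expected in 19 | 0.04 | 0.08 | 0.17 |
| Expected in 28 | 0.06 | 0.12 | 0.26 |
| Chance of no event in 47 | 91% | 82% | 65% |
| Expected in 47, early hazard tripled | 0.30 | 0.61 | 1.27 |
| Chance of at most 2 events, early hazard tripled | 99.7% | 97.7% | 86.5% |

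**What it would take to reach p<0.05.** These are uncorrected chi-square p-values, the version most favourable to finding a difference:

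- 1/19 vs 0/28: 0.220
- 0/19 vs 1/28: 0.405
- 1/19 vs 1/28: 0.778
- 2/19 vs 0/28: 0.079
- 0/19 vs 2/28: 0.234
- 3/19 vs 0/28: 0.030
- 0/19 vs 5/28: 0.051
- 0/19 vs 6/28: 0.031

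So no split of one or two events is significant. With none in the other group, at least 3/19 (16%) or 6/28 (21%) is needed. Fisher's exact test needs 4/19 or 7/28.

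**If no event is seen.** The exact 95% upper limit is 1 − 0.025^(1/n): 17.6% for 0/19 and 12.3% for 0/28. A double zero excludes little.

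**A different starting point.** Assuming the 30-day risk directly, 0.1%, 0.5%, 1% or 2% gives 0.05, 0.24, 0.47 or 0.94 expected events in 47. With a base risk of 1% or less, exact power of the uncorrected chi-square is below 0.5% for a doubling in either group and below 3% for a fourfold difference. At 2% the highest values are 2.2% and 11.3%.

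**Reading 2: common date.** A patient operated on 1 month before that date has a chance 1 − exp(−h) of having recurred: 0.21%, 0.44% or 0.93%. At 24 months it is 5%, 10% or 20%. The ratios are 23.4, 22.8 and 21.6. The yes/no variable does not record which kind of patient is being counted.

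**Reading 3: fixed later time.** Taking 12 months for illustration only, the risk 1 − exp(−12h) is 2.5%, 5.1% or 10.6%, or 1.2, 2.4 or 5.0 events in 47, with equal time at risk.

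**The case against.** The 30-day sentence is confined to short-term outcomes and does not say that recurrence is scored then. The sentences on regular intervals carry no 30-day limit, so a longer but unstated follow-up is a fair reading. This stands, and it is why the defect is a missing horizon, not a declared 30-day recurrence endpoint. It does not rescue the plan, because no other horizon appears anywhere.

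The 22- to 23-fold ratio under the second reading follows almost directly from dividing 24 months by 1 month, and it contrasts two individuals, not two groups. If surgery dates are spread alike in both groups, unequal time at risk produces no systematic difference between them. This also stands: no between-group bias is shown, because the documents do not give surgery dates by group.

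Sample size is a problem at any horizon. For assumed differences such as 5% vs 10%, 5% vs 15% or 20% vs 10%, 19 vs 28 patients give about 8% to 17% power by the normal approximation. Stating a horizon therefore removes the ambiguity but does not make the comparison strong, which is a reason for reporting recurrence descriptively.

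Finally, recurrence is in neither aim, and leakage and infection also lack definitions. That limits the weight. But those two outcomes can be observed within the stated window, whereas recurrence in practice cannot.

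**Conclusion.** The concern holds. Local recurrence is a listed and compared outcome without a horizon, and the one follow-up length in the document cannot support the comparison. That no horizon is stated rests on the text alone. That 30 days is uninformative rests on assumed rates, but fewer than one event is expected in 47 patients across two-year risks of 5% to 20% at a constant hazard and across assumed 30-day risks of 0.1% to 2%. Tripling the early hazard at the highest two-year risk raises this only to 1.27. The size of any distortion under a common cut-off date cannot be determined from the documents. The point should be fixed, but it affects one outcome outside the stated aims and leaves the leakage and surgical site infection comparisons as they are.

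**What to change.** Remove local recurrence from the outcomes compared at 30 days, and state which of the listed outcomes that window covers.

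Alternatively, if later records exist, keep recurrence as a separate descriptive outcome with a stated horizon, definition and method of ascertainment. If follow-up to that horizon is complete, report a proportion with a 95% confidence interval in each group. If it is not, use Kaplan-Meier, or cumulative incidence with death as a competing event, with 95% confidence intervals and numbers at risk. In either case, state that a non-significant result will not be read as showing no difference.

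Removing the outcome, or stating its horizon and definition, is a text edit. Keeping it needs follow-up records beyond 30 days; the documents describe no recurrence-specific follow-up, so that cost cannot be stated from them. The downside is that one listed outcome is dropped or becomes descriptive only.

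### Aim 1 is worded as an effect of ileostomy, but a 19 v 28 cohort with no stated assignment rule and only unadjusted tests supports association at most

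*Combined protocol and SAP*

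**What the plan says.** - **Title:** "The Effects of temporary ileostomy on outcome in" patients with rectal cancer. The same title calls the study a comparative cohort.
- **Background, aim 1:** "to evaluate the effect of temporary ileostomy on the occurrence of AL". Aim 2 only compares complications, so the causal wording is in the title and aim 1.
- **Methodology, Patients:** "Patients are assigned to group I (19 patients) who will undergo temporary ileostomy, and group II (28 patients") without one. No randomisation, clinical criterion, or surgeon or patient choice is described.
- **Background, risk factors:** "Risk factors for AL include more distal anastomoses, neoadjuvant pelvic radiation therapy, male gender, prolonged operative time, advanced stage of tumor", and also "multiple firings of linear stapler across rectal stump".
- **Data collection:** age, sex, stage, preoperative radiotherapy and anastomosis type are recorded. Duration of surgery is recorded as an outcome. Anastomotic height and number of stapler firings are not on the list.
- **Statistical Analysis Plan:** descriptive statistics, t tests, and for the binary leakage outcome "To examine the relationships and comparisons between the two groups, the chi-square test was used". There is no regression, stratification, matching or sensitivity analysis, and no statement limiting conclusions to association.

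**The concern.** A chi-square test on leakage compares two groups of patients. It isolates what the stoma did only if the groups had similar leak risk beforehand. Nothing in the design secures that, and the protocol itself lists factors on which they could differ. A leakage difference, or its absence, could then reflect who was given a stoma. At stake is the answer to the first aim, on a procedure whose role the Background describes as debated. Followed as written, the plan would let a crude p-value from 47 patients be reported as an effect.

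**Working it through.** The plan gives no figure for bias or comparability, so there is none to reproduce. The check has four steps.

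**1. Risk factors against their role in the plan**

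| Named leak risk factor | Collected? | Adjustment role |
|---|---|---|
| Male sex | yes | none |
| Advanced stage | yes | none |
| Preoperative pelvic radiotherapy | yes (radiotherapy, yes/no) | none |
| Operative time | as an outcome | none |
| More distal anastomosis | not listed | none |
| Multiple stapler firings | not listed | none |

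**2. How far imbalance could move the crude odds ratio (OR)**

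Assumptions, not document figures: one binary risk factor with OR c = 2, 3 or 4; leak risk 8% in group II patients without it; true stoma OR t = 0.5; factor prevalence h1 with stoma, h2 without. Let o = 0.08/0.92 = 0.0870 and r(x) = x/(1+x).

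- Group I risk: h1·r(o·t·c) + (1−h1)·r(o·t)
- Group II risk: h2·r(o·c) + (1−h2)·r(o)

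Example, 80% v 20%, c = 4:
- Group I = 0.8×0.1481 + 0.2×0.0417 = 0.1269
- Group II = 0.2×0.2581 + 0.8×0.0800 = 0.1156
- Crude OR = (0.1269/0.8731)/(0.1156/0.8844) = 1.11

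| Prevalence, stoma v none | c = 2 | c = 3 | c = 4 | Power of baseline chi-square test |
|---|---|---|---|---|
| 50 v 40 | 0.54 | 0.57 | 0.59 | 11% |
| 60 v 30 | 0.62 | 0.70 | 0.77 | 55% |
| 60 v 20 | 0.67 | 0.80 | 0.90 | 81% |
| 80 v 30 | 0.70 | 0.84 | 0.94 | 95% |
| 80 v 20 | 0.75 | 0.95 | 1.11 | 99% |

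With the factor commoner in the no-stoma group, 40 v 50 gives 0.45 to 0.47, and the large imbalances reversed give 0.23 to 0.41. If the true OR is 1.0, mild imbalance gives 1.07 to 1.14, or 0.88 to 0.93 reversed.

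Baseline risk matters little. At 3% and 21%, the 50 v 40 range becomes 0.54–0.58 and 0.54–0.61, and the large-imbalance range 0.62–1.08 and 0.62–1.16.

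**3. What a baseline test would reveal**

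The last column sums the binomial probabilities of all tables at 19 v 28 for which the uncorrected chi-square gives p < 0.05. Power is low for mild to moderate imbalance and high for the imbalances that could hide a halving of the odds. It says nothing about factors that are not recorded.

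**4. How much information there is**

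- Expected leaks at the Background's 3% to 21%: 47×0.03 = 1.4 to 47×0.21 = 9.9.
- Hypothetical 2/19 v 5/28 leaks: conditional OR 0.55, exact 95% CI 0.05 to 3.86.
- Approximate standard error of a standardised difference: √(1/19 + 1/28) = 0.30.
- Firth-penalised logistic model, simulated cohorts of 19/28 with at least 5 leaks, 8% baseline risk, true OR 0.5, model with group, the risk factor and one unrelated covariate. At 80 v 30 with c = 4, adjustment moves the estimated OR from 0.91 to 0.49, and root mean squared error (RMSE) of the log OR from 1.05 to 1.01. At 80 v 30 with c = 2, RMSE rises from about 0.94 to 1.02.

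**The case against.** **Collected factors may have a use.** The SAP's descriptive statistics and its tests between groups can naturally be read as covering a baseline comparison. That stands: what is missing is an adjustment role, not every role.

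**Baseline tests are not uninformative.** A reader might infer that at 19 v 28 they would miss any imbalance that matters. The table does not support that: power is 81% to 99% at 60 v 20, 80 v 30 and 80 v 20. The limits are moderate imbalance and unrecorded factors.

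**The operation is standardised.** Resection is described for all patients as "up to the level of the pelvic diaphragm, sparing the autonomic nerves". This may narrow variation in anastomotic height. It does not balance sex, stage or radiotherapy.

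**Adjustment cannot rescue so few events.** Largely right. With about 1 to 10 expected leaks, a model reduces bias from the factor it contains, widens the interval, can raise total error, and leaves unmeasured factors untouched. The documents do not support calling multivariable adjustment the necessary remedy.

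**Asking a causal question of a cohort is legitimate, and rewording removes no confounding.** True, provided the limits are stated. This plan states none, and the title's cohort label alone does not limit the conclusion.

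**Conclusion.** The point holds, as a should-fix. Title and aim 1 claim an effect, the assignment rule is not given, and every planned test is unadjusted. The leakage comparison can support an association at most.

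The size of the problem is unknown. Under the assumptions above it runs from trivial (0.5 seen as 0.45 to 0.59) to enough to hide a halving of the odds (0.62 to 1.11) or exaggerate it (0.23 to 0.41). These are illustrations, not estimates for this cohort.

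Two stronger readings are tempting and unsupported. One is that stomas went to higher-risk patients, so the crude result understates a benefit; without an assignment rule the documents fix no direction. The other is that the comparison is already shown to be biased; no baseline or outcome data are given, so only the absence of protection is established.

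**What to change.** **Recommended**
1. Word the title, aim 1 and the eventual conclusions as association, and state that the crude leakage result cannot be read causally.
2. Describe how patients came to each group in practice.
3. Report age, sex, stage, radiotherapy and anastomosis type by group with standardised differences. Set no pass/fail cut-off, since their standard error is about 0.30.
4. Report the crude leakage OR with an exact 95% CI beside the p-value.

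These cost wording, one table and one interval, and use only variables already on the data list.

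**Optional and exploratory**

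A Firth-penalised logistic model for leakage, preferably group plus preoperative radiotherapy alone given the expected event count. Fix the covariate without sight of leakage. Do not adjust for duration of surgery, which is listed as an outcome and may itself be changed by making the stoma. The protocol mixes tenses ("outcomes were compared between two groups"), so label the model post hoc if outcomes have been seen. State its downsides with it: a wider interval, no protection against unmeasured factors, and possibly more total error when the risk factor is weak, even under large imbalance. The SAP names SPSS without a version, so this model may need an add-on or second package (assumption).
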